**Primary Exclusion Criteria include but are not limited to:**

Cardiovascular:	myocardial infarction, coronary artery disease, peripheral vascular disease, arrhythmia, congestive heart failure, valvular disease, hypertension
Respiratory:	bronchitis, chronic obstructive pulmonary disease, smoking, shortness of breath
Hepatic:	hepatitis, jaundice, ascites
Neurologic:	seizure, stroke, positive neurologic findings on neurologic examination, multiple sclerosis, Meniere's disease, Parkinson's disease, neuropathy, peripheral stenosis
Gastrointestinal:	esophageal reflux, hiatal hernia, ulcer
Endocrine:	diabetes, thyroid disease
Renal:	acute or chronic severe renal insufficiency
Hematologic:	blood dyscrasias, anemia, coagulopathies, on anticoagulant therapy
Musculoskeletal:	prior surgery or trauma to head neck or face, arthritis, personal or family history of malignant hyperthermia
Psychiatric:	history or treatment for an active psychiatric problem, depression
Reproductive:	pregnancy, breast-feeding
Medications:	regular use of prescription and non-prescription medications expected to affect CNS function, St. John's Wort
Allergies:	labetalol, ondansetron, glycopyrrolate, ketamine, midazolam

**Patients will be excluded from our study if they fail to pass a drug test that screens for the following: Cocaine (COC), d-Amphetamine (AMP), d-Methamphetamine (Mamp), Tetrahydrocannabinol (THC), Methadone (MTD), Opiates (OPI), Phencyclidine (PCP), Barbiturates (BAR), Benzodiazepines (BZO), Oxycodone (OXY)**

**Recruitment:** We will select 15 volunteer subjects (male and female) between the ages of 18-45 years.

The subjects will be recruited using:

An announcement of the study distributed through the Partners Public Affairs distribution list.

The MGH Research Study Volunteer Program (RSVP).

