During this period, a calibrated cuff pain stimuli will be delivered to the gastrocnemius area of the lower leg using a validated cuff pain device (Hokanson Rapid Cuff Inflator), titrated to 8-9/10 pain. One advantage of using cuff algometry pain is that, unlike more superficial methods (e.g. heat pain), cuff pain responses are unaffected by sensitization or desensitization of the skin. The following questionnaires will be administered to assess pain intensity and quality: 1) PROMIS Numeric Rating Scale V1.0 – Pain Intensity 1A; 2) PROMIS Scale v2.0 – Neuropathic Pain Quality 5a; and, 3) PROMIS Scale v2.0 – Nociceptive Pain Quality 5a. Participants will be oriented to the following pain scale: (1) 0-1 out of 10 as “tolerable”; (2) 2-3 out of 10 as “slight discomfort”; (3) 4-7 out of 10 as “moderate discomfort”; (4) 8-9 out of 10 as “painful”; and (5) 10 as “maximum pain”.

**B. Baseline:** A 10 to 15-minute period of EEG recording will be obtained for EEG calibration (i.e. eye movements, eye blinks, facial muscle movement) and EEG normalization (awake-eyes closed). Recordings of physiological measurements (blood pressure, heart rate, pulse oximetry, end-tidal carbon dioxide, electrooculogram, electromyogram and galvanic skin response) will be initiated and maintained from the beginning of the study protocol until the subject is ready for discharge.

**C. Loss consciousness:** 2mg/kg of ketamine will be infused (Medfusion pump) over approximately 5 minutes to gradually induce and allow for rapid emergence from ketamine-anesthesia. This anesthetic dose is expected to cause approximately 10-15 minutes of loss of consciousness/responsiveness. Subjects will be asked to respond to auditory stimuli via button-press jittered at random between 4 and 8 second intervals in order to resolve the precise period at which loss and recovery of consciousness/responsiveness occurred at a fine temporal scale.

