**Behavioral Analysis:** The probability of response to verbal stimuli and the difference in probability of response will be estimated by using Bayesian Monte Carlo methods to fit a state-space model to these data. To perform group-level analyses, we will align the behavioral data across subjects with respect to each subject's LOC time for induction and with respect to each subject's ROC time for emergence. We will then pool the responses, and pooled data will be used to estimate group-level probabilities of response using the state-space model.

**Inflammatory profile Analysis:** Plasma samples will be submitted to Myriad/Rules Based Medicine (Myriad RBM, Austin, TX, USA) for analysis using their proprietary platform. Wilcoxon rank-sum tests with corrections for multiple comparisons will be used to assess analyte differences. In exploratory analyses, we will examine Pearson correlations between analytes and variables of interest (i.e. pain, anxiety).

**Power Analysis:** Assuming the point estimate for gamma power at baseline is -20 dB and 5 dB for ketamine induced-unconsciousness (**Fig 2.**), a standard deviation of 20 dB, type 1 error of 0.05, and desired power of 0.9,  $n=14$  study volunteers will enable us to detect a gamma power ratio of 25 dB. Therefore, we aim to recruit up to 15 subjects.

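### The group response curve is fitted to pooled responses with no subject-level term, so its interval reflects the number of stimuli rather than the 15 volunteers and is too narrow where aligned subjects still differ

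*Combined protocol and SAP*

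**What the plan says.** Section 6, Behavioral Analysis, says that the response probability, and differences in it, "will be estimated by using Bayesian Monte Carlo methods to fit a state-space model to these data". For the group level, "we will align the behavioral data across subjects with respect to each subject's LOC time for induction", and likewise to ROC for emergence. The next sentence is: "We will then pool the responses, and pooled data will be used to estimate group-level probabilities of response using the state-space model".

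Section 5, part C, gives the stimulus spacing as "jittered at random between 4 and 8 second intervals" and the expected unresponsive period: "This anesthetic dose is expected to cause approximately 10-15 minutes of loss of consciousness/responsiveness". Section 3, Recruitment, gives the number of independent units: "We will select 15 volunteer subjects".

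The documents mention no random effect, hierarchical model or resampling of subjects for the behavioral data. They also state no interval level and no rule for calling a response probability zero or non-zero. By contrast, the Spectral Analysis paragraph of section 6 summarises the group spectrograms by the median across subjects, which makes the subject the unit.

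**The concern.** A state-space model lets one common response probability drift over time. Given that common state, it treats the pooled responses at each moment as draws with the same probability. Volunteers who settle at different response rates, or who pass through the transition more or less steeply, break that assumption: one person's responses resemble each other for minutes at a time. The pooled fit has no term for this, so it counts each stimulus as new information about the population.

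The group curve describes how responsiveness is lost and regained under ketamine. If its band omits between-subject variance, it shows how precisely these 15 people were measured together, not how far the curve could move with another 15 volunteers. The stretch after ROC is the most exposed, because responding is partial there and people can differ in level.

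**Working it through.** **The plan's own figure.** No interval or sample size is stated for the behavioral analysis. The only computed figure, n=14, concerns gamma power. It reproduces from the two-sided two-sample normal formula, 2 × [20 × (1.960 + 1.282) / 25]² = 13.45, rounded up to 14. It has no bearing on this point.

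**Inputs.** From the documents: 15 subjects, stimuli 4 to 8 s apart, 10-15 minutes of unresponsiveness. Assumed: a mean spacing of 6 s (the midpoint) and a range for the ICC, the share of the variance of a single response that is due to lasting differences between subjects.

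**Step 1: stimuli against subjects.** Ten minutes gives 600/6 = 100 stimuli per subject and 15 × 100 = 1,500 pooled stimuli from 15 independent units.

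**Step 2: averages over a period.** For a mean over m stimuli per subject, the variance is inflated by 1 + (m − 1) × ICC, and the interval should be wider by the square root of that. With m = 100:

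| ICC | Variance inflation | Interval should be wider by | Effective number of stimuli |
|---|---|---|---|
| 0.01 | 1.99 | 1.4 | 754 |
| 0.05 | 5.95 | 2.4 | 252 |
| 0.1 | 10.9 | 3.3 | 138 |
| 0.3 | 30.7 | 5.5 | 49 |

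The same formula for a one-minute window (m = 10) gives √(1 + 9 × 0.1) = 1.4 and √(1 + 9 × 0.5) = 2.3. A nominal 95% interval would then cover about 84% and 60%. These one-minute figures are illustrative only: they describe a simple proportion, not the planned smoother.

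**Step 3: the pointwise band of the pooled model, aligned data.** Simulations used 15 subjects sharing the same transition time, one state-space model fitted to the pooled counts, and a nominal 95% band compared with the true population-average probability after ROC.

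| How subjects differ | Coverage (ICC) |
|---|---|
| Level, as a lasting shift on the logit scale (150 runs per setting) | 99% (0), 96% (0.05), 90% (0.17), 84% (0.29), 74% (0.40) |
| Slope and plateau (100 runs per setting) | 99% (0), 98% (0.04), 94% (0.14), 90% (0.26), 89% (0.37) |
| Plateau | 98% (0.04), 97% (0.14), 85% (0.37), 84% (0.53) |

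In the first row the mean band width was 0.211 against 0.255 needed at ICC 0.17 (0.255/0.211 = 1.2 times too narrow). It was 0.190 against 0.328 at ICC 0.40 (0.328/0.190 = 1.7 times). With no subject differences the smoother covers 99%, so it starts conservative, which is why small ICCs do no visible harm.

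The first row's model also undercovers before ROC (93.2%, 81.5% and 68.7% at logit SD 1, 1.5 and 2). That happens because it lets some subjects keep responding at that stage, and a period marked out as unresponsive leaves less room for this.

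**Step 4: no responses at all.** If nobody responds over 10 minutes, the one-sided 95% upper bound is 1 − 0.05^(1/1500) = 0.20% per stimulus when all stimuli count as independent. With 15 subjects as units, the bound on the share of subjects who would respond is 1 − 0.05^(1/15) = 18.1%. These are different quantities; the second is the one that speaks to a further volunteer.

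**The case against.** The strongest objection is that the plan aligns before it pools. This stands, and it limits the point. A reader might simulate a mean logit rising from −3 to +3 over 10 minutes with a random subject intercept and no alignment. Coverage then comes out at about 89%, 73% and 59% for an intercept SD of 1, 2 and 3, and the reader might infer that the planned band is badly wrong. The documents do not support that. On a line rising 0.6 logits per minute, an intercept b is a time shift of b/0.6 minutes, so those SDs are onset differences of 1.7, 3.3 and 5.0 minutes, which alignment is there to remove. Aligned to each subject's true 50% crossing, coverage was 99% at every SD; aligned to a noisily detected ROC, it was 95-96%. What survives is difference in slope and level. With intercept SD 2 and slope log-SD of 0.3, 0.6 and 1.0, coverage was 98%, 97% and 92% with true alignment, and 95%, 93% and 88% with noisy alignment.

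A reader might also infer that the tests of Aim 1 are invalid. That goes too far. Hypotheses 1.1 and 1.2 concern response probability within EEG patterns, whereas the pooled curve is indexed to LOC and ROC. The plan attaches no band level and no decision rule to the curve, and the study is sized on gamma power. The point is about the interval this model would produce, not one the plan quotes.

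Finally, the opening sentence of the paragraph can be read as allowing per-subject fits. That is fair, but the group-level step still pools raw responses.

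**Conclusion.** The direction is established: with no subject-level component, the group-level interval is too narrow whenever aligned volunteers still differ in response level or slope. The size is not established, because the documents give no between-subject variance.

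Under assumed values with aligned data, a nominal 95% pointwise band is adequate at an ICC of about 0.05 or less, covers roughly 90-97% at about 0.15, and roughly 74-89% at about 0.4. Averages over a period are affected more: over 10 minutes the interval should be 2.4 to 3.3 times wider at an ICC of 0.05 to 0.1. These figures rest on 15 subjects, 6-s spacing and the simulated curve shapes.

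This is a moderate point. It should be settled before analysis, but it does not undermine the design.

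**What to change.** Replace the pooling sentence in section 6, Behavioral Analysis, with:

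> Group-level response probability will be estimated from the aligned data with a hierarchical state-space model with subject-level random effects, fitted by the same Bayesian Monte Carlo method, or with intervals obtained by resampling whole subjects. Individual response curves will be shown with the group curve.

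Name in advance which of the two is the main method. The random effects should cover level and slope, since a shift in timing is already handled by alignment. If no volunteer responds in some stretch, resampling returns an interval of zero width; there, report how many of the subjects responded at least once, with an exact bound.

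The cost is a change of wording, a little more programming and somewhat wider intervals. No new data or procedures are needed. If subjects turn out to differ little, the hierarchical model will show that and little precision is lost.

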Unfortunately, this study and those from other research groups have not provided information on how the spatio-temporal dynamics of ketamine-induced oscillatory dynamics relate to loss of consciousness, return of consciousness or hallucinatory states. This is because ketamine has been administered in a bolus fashion in these studies. Ketamine-induced EEG dynamics may aid principled approaches to brain state monitoring and targeting during general anesthesia. They may also lend insights into anti-nociceptive or pain mechanisms. Additionally, parallels between ketamine-induced hallucinatory states and clinical diagnoses associated with hallucinatory states (i.e. schizophrenia) may lend mechanistic insights into abnormal brain functioning.

Therefore, we aim to study the association between ketamine-induced neural oscillations, altered states of arousal and the perception of painful stimuli. Our central hypothesis is that ketamine-induced neural oscillations will exhibit clear distinctions between altered arousal states. Our study cohort will be comprised of healthy volunteers. We will perform assessments for hallucinations, anxiety and pain. At the conclusion of this study, we will have expanded our knowledge of the neurophysiology associated with ketamine-induced altered arousal states. The proposed human study is an integral component of our NIH P01 grant "Integrated Systems Neuroscience Studies of General Anesthesia (5 P01 GM118269) that is structured to study ketamine-induced neurophysiological dynamics across scales using recordings obtained from rodents and non-human primates, and from computational models derived from dynamical systems modeling.

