## 2. SPECIFIC AIMS

**AIM 1:** To use high-density EEG recordings to characterize the different brain states induced by ketamine

**Hypothesis 1.1.** Ketamine gamma-burst pattern will be associated with a zero probability of response to auditory stimuli

**Hypothesis 1.2.** Ketamine gamma-stable pattern consists of two distinct brain states: an anesthetic state with zero probability of response to auditory stimuli and a hallucinatory state with non-zero probability of response to auditory stimuli

**AIM 2:** To use high-density EEG recordings to characterize oscillatory dynamics associated with the analgesic effect of ketamine

**Hypothesis 2.1.** Ketamine theta power will correlate with analgesia

**Hypothesis 2.2.** Ketamine gamma power will not correlate with analgesia

**AIM 3:** To use inflammatory profiling of serum to understand the effect of ketamine on systemic inflammation

**Hypothesis 3.1.** Ketamine-anesthesia will be associated with decreased levels of pro-inflammatory cytokines interleukin 6 and TNF-alpha

**Hypothesis 3.2.** Levels of pro-inflammatory cytokines interleukin 6 and TNF-alpha will correlate with a decrease in perception of painful stimuli

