**4. SUBJECT ENROLLMENT**

**Procedure for informed consent:** Prior to the study, each subject will sign informed consent (detailed in Screening Visit subsection of Study Design Section below). The investigator obtaining consent will explain in detail the protocol of the study, its purpose and potential benefits to society. Subjects will be informed that if they feel uncomfortable with the study, they can choose to terminate the study at any time.

**Treatment Assignment and Randomization:** Not applicable

**Retention:** All subjects who provide verbal or written consent but later decline participation in the study will not be subject to any study-related follow-up.

**Remuneration:** For successful completion of this protocol, subject remuneration will be \$500. The subject will also be compensated for the cost of parking for their study visit.

**Location:** These studies will take place on White 5 at the Carl Rosow Center for Clinical Research. White 5, which is located in the cardiac anesthesia office suite, was constructed specifically for the performance of research on human subjects receiving the depressant medications used in anesthesia. The research area is built to the same standard as a typical surgical procedure room at MGH with respect to ventilation, temperature control, plumbing and electrical facilities, as well as storage. There is piped oxygen and air, wall suction and waste anesthetic gas removal. The hospital's backup generator supports electrical outlets in this location. There is a fully equipped anesthesia machine, standard anesthetic care monitors and a fully equipped code cart. The code cart and medications are checked at intervals by personnel from the OR pharmacy, and the anesthesia equipment is safety checked and maintained by Anesthesia Bioengineering. Research subjects receiving anesthetic drugs in this unit are given an identical standard of care as patients in MGH operating rooms.

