**Study Visit:** During the study, a board-certified anesthesiologist will be present whose sole responsibility will be to monitor (check) your safety. The sequence of this study visit will be as follows: arrival (approximately 45 minutes), baseline (approximately 15 minutes), loss of consciousness (approximately 15 minutes), recovery of consciousness (approximately 60 minutes), and discharge (approximately 45 minutes). We anticipate the study to last approximately 3 to 5 hours.

**A. Arrival:** Confirmation of the study subjects' fasting status (minimum 8 hours) will be made. A urine sample will be obtained for pregnancy testing in all female study subjects. The following assessments will be performed: 1.) Clinician Administered Dissociative States Scale (CADSS) to assess for hallucinations; 2.) Promis Item Bank v.1.0 – Emotional Distress-Anxiety Short Form 8A modified to ask for symptoms experienced within the past hour; 3.) Promis Item Bank v.1.0 – Meaning and purpose Short Form 8A; and, 4.) Promis Item Bank v.1.0 – Positive Affect Short Form 15A (modified to ask for symptoms experienced within the past hour). The following computer presented neurocognitive assessment tests will also be performed: Global Precedence, Operation Span and Columbia Card tasks will also be administered (<https://www.neurobs.com>).

Standard monitors for anesthesia care monitoring including blood pressure (cuff), electrocardiogram, capnography and pulse oximetry and a 64-channel EEG montage will be placed on the subject. Video of the study subject may be recorded during baseline, induction and recovery from hypnosis periods to assess the study subject's level of arousal. Permission to record video for data analysis purposes will be obtained from the research consent form. An intravenous line will be placed for drug administration, and we will obtain approximately 15ml of blood (baseline pre-ketamine).

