After the third assessment (i.e. approximately 35 minutes after recovery of consciousness), we will administer 0.05 mg/kg of midazolam (maximum dose of 4 mg) to resolve ketamine-induced perceptual disturbances. Midazolam is routinely administered during the peri-operative period to mitigate ketamine-induced perceptual disturbances. Approximately 5 minutes after midazolam is administered, we will resume assessments for a minimum of two assessments (approximately 55 minutes after recovery of consciousness) or until the subject is ready for discharge. We will obtain approximately 15ml of blood (post-ketamine, pre-midazolam). The following computer presented neurocognitive assessment tests will also be performed: Global Precedence, Operation Span and Columbia Card tasks will also be administered (post-ketamine, pre-midazolam).

**E. Discharge:** If medically stable, as deemed by a board-certified anesthesiologist, the intravenous line and physiological monitoring devices will be discontinued, and subjects will be discharged home with a responsible family member or other adult caretaker. Discharge home will be based on criteria established by the MGH Department of Anesthesia practices for discharge from the hospital following ambulatory surgery. The subject must have stable vital signs, be able to respond appropriately to normal commands, be pain free, be free from any nausea and vomiting and have no bleeding from the intravenous sites. Subjects must be able to walk unassisted and have an accompanying adult to escort them home. Subjects will be advised against returning to work and driving or operating heavy equipment for 24 hours.

If subjects experience adverse events at home, they will be referred for evaluation at the nearest emergency department. These instructions will also be provided to the responsible adult escort prior to discharge. The subject's individual insurance plan will be responsible for covering this visit.

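### IL-6 and TNF-alpha are measured twice in the same volunteers, but the plan compares them with a test for two independent groups

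*Combined protocol and SAP*

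**What the plan says.** Section 6, under Inflammatory profile Analysis, gives the rule for the serum markers: "Wilcoxon rank-sum tests with corrections for multiple comparisons will be used to assess analyte differences". It does not say which samples are compared, how many analytes are tested, or which correction is used. Only the Pearson correlations that follow are called exploratory.

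The rest of the document fixes what can be compared:

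- Section 2, Hypothesis 3.1, is directional: "Ketamine-anesthesia will be associated with decreased levels of pro-inflammatory cytokines interleukin 6 and TNF-alpha".
- Section 1 describes a single cohort: "Our study cohort will be comprised of healthy volunteers".
- Section 4 has no second arm: "Treatment Assignment and Randomization: Not applicable".
- Section 5, Arrival, has the first study-visit draw: "we will obtain approximately 15ml of blood (baseline pre-ketamine".
- Section 5, Recovery of consciousness, has the second: "We will obtain approximately 15ml of blood (post-ketamine, pre-midazolam".

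The only power calculation concerns EEG gamma power: "study volunteers will enable us to detect a gamma power ratio of 25 dB". Nothing comparable is given for Aim 3.

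**The concern.** The rank-sum test takes its null distribution from two sets of values that are all mutually independent. Here the two sets are the before and after values of the same people. If someone with a high baseline tends to have a high second value, much of the spread between volunteers cancels in the within-person difference. The rank-sum test does not use that cancellation. It judges the shift against a variance that is too large, so its p-values are too large.

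The harm is therefore in the false-negative direction. Hypothesis 3.1 would be tested in at most 15 volunteers, with a multiplicity correction on top. If IL-6 or TNF-alpha showed no significant fall, a reader could not tell whether ketamine had no effect or the test had discarded the pairing.

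**Working it through.** **1. Which comparison is available.** One cohort, no assignment and two study-visit draws per volunteer leave one contrast for Hypothesis 3.1: after minus before, within person. This step needs no assumption.

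**2. The plan's own sample size.** Inputs from Section 6: difference 25 dB, SD 20 dB, type I error 0.05, power 0.9. The two-sided formula for two independent means gives

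n = 2 × (1.960 + 1.282)² × 20² / 25² = 2 × 10.51 × 0.64 = 13.4, rounded up to 14.

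This reproduces the stated 14. It concerns gamma power only. It supplies no cytokine effect size, SD or within-subject correlation, so those inputs below are assumptions and are shown as ranges.

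**3. Direction and rough size by hand.** Let σ be the SD of a single measurement, ρ the within-subject correlation and n the number of pairs. The variance of the mean difference is 2σ²/n if the samples are treated as independent, but 2σ²(1 − ρ)/n in truth. A nominal two-sided 5% test that ignores the pairing therefore has an actual type I error of about 2Φ(−1.96/√(1 − ρ)):

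- ρ = 0.3: 1.96/√0.7 = 2.34, giving 1.9%
- ρ = 0.5: 1.96/√0.5 = 2.77, giving 0.6%
- ρ = 0.7: 1.96/√0.3 = 3.58, giving 0.03%

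This is a normal approximation for means; the exact rank tests come next.

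**4. Simulation.** Assumptions: 15 pairs (the recruitment target), bivariate normal values with equal SDs, exact two-sided tests, 40,000 replicates per setting, shift in SDs of a single measurement.

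Actual type I error at nominal 5%:

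| Correlation | Rank-sum | Signed-rank |
|---|---|---|
| 0 | 4.4% | 4.7–5.0% |
| 0.3 | 2.1% | 4.7–5.0% |
| 0.5 | 0.8% | 4.7–5.0% |
| 0.7 | 0.1% | 4.7–5.0% |

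The signed-rank column gives its range over all four settings. Repeat runs gave 1.9 to 2.1% for the rank-sum test at 0.3 and 0.1 to 0.2% at 0.7.

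Power, rank-sum v signed-rank:

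| Shift | ρ = 0 | ρ = 0.3 | ρ = 0.5 | ρ = 0.7 |
|---|---|---|---|---|
| 0.5 SD | 0.24 v 0.23 | 0.20 v 0.31 | 0.18 v 0.42 | 0.14 v 0.62 |
| 0.8 SD | 0.52 v 0.50 | 0.52 v 0.65 | 0.54 v 0.80 | 0.56 v 0.95 |
| 1.0 SD | 0.72 v 0.70 | 0.75 v 0.84 | 0.78 v 0.94 | 0.83 v 0.99 |
| 1.25 SD | 0.89 v 0.87 | 0.92 v 0.96 | 0.95 v 0.99 | 0.97 v 1.00 |

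At 0.8 SD the loss is 0.65 − 0.52 = 0.13, 0.80 − 0.54 = 0.26 and 0.95 − 0.56 = 0.39 as the correlation goes from 0.3 to 0.7. At 1.25 SD it is only 0.03 to 0.04. At zero correlation there is none.

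**5. Sensitivity, at 0.8 SD (rank-sum v signed-rank).**

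- Level 0.025, an assumed Bonferroni split over the two named cytokines: 0.39 v 0.68 at ρ = 0.5; 0.38 v 0.89 at ρ = 0.7.
- 14 pairs, 5% level: 0.52 v 0.78 at ρ = 0.5; 0.54 v 0.94 at ρ = 0.7.
- Heavy tails (bivariate t, 4 df), ρ = 0.5: 0.71 v 0.87.
- Lognormal values (assumed log-SD 0.8, shift on the log scale), ρ = 0.5: rank-sum 0.54, signed-rank on the raw change 0.75, signed-rank on the log-ratio 0.80.

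The direction does not depend on normality.

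**The case against.** **It may be a slip of the pen.** The two Wilcoxon tests are easily confused, and an analyst with no second group would soon notice the pairing. That may well be so, but the sentence names the unpaired test and someone following it would run it. If it is a slip, correcting it is easier still.

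**The size of the loss is assumed.** This stands. The documents give no cytokine SD, effect or correlation. The loss is small for a very large shift. For a shift of 0.5 SD at correlation 0.3, even the signed-rank test reaches only 0.31, so a null result would be weak under either test. The figures show a range, not a forecast. A positive correlation is nevertheless the reasonable expectation for two samples from one person within a visit planned for 3 to 5 hours.

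**The paired test has a price when the correlation is near zero.** This also stands. At zero correlation the signed-rank test gives up about 0.02 in power at the 5% level and up to about 0.06 at 2.5%. The plan does not limit the analyte family to two, and a stricter level raises the price: at an assumed level of 0.001 and zero correlation, power is 0.40 v 0.26 for a 1.25 SD shift and 0.63 v 0.45 for 1.5 SD. From a correlation of 0.3 upward, the signed-rank test was ahead in every setting run.

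**A significant rank-sum result would be safe anyway.** This holds if the correlation is positive or zero. At −0.2 the rank-sum type I error is 6.5%, though a negative correlation is implausible here.

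**Conclusion.** The concern holds. The named test does not fit a design in which the only available cytokine comparison is within volunteer, and that conclusion rests on the text alone. The consequence is lost power rather than false positives, provided the two values are positively correlated. With 15 pairs, a two-sided 5% level and assumed correlations of 0.3 to 0.7, the loss is 0.11 to 0.48 in absolute power at 0.5 SD, 0.13 to 0.39 at 0.8 SD and 0.09 to 0.16 at 1.0 SD. It becomes small at 1.25 SD and vanishes at zero correlation. This should be corrected before analysis. It does not affect the EEG aims.

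**What to change.** In Section 6, replace the rank-sum sentence with one stating that each analyte will be compared before and after ketamine by a two-sided Wilcoxon signed-rank test on each volunteer's change. Specify the log-ratio of the two values if the analytes are expected to be right-skewed, and make that choice before the data are seen.

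As an optional clarification in the same sentence, name the multiplicity method and the family it covers, for example the two cytokines in Hypothesis 3.1, with other analytes reported separately as exploratory. A small family also limits the price of the paired test near zero correlation.

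The cost is one sentence. No new samples, visits or volunteers are needed.
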